2. LIST OF ABBREVIATIONS AND DEFINITIONS OF TERMS

RA: rheumatoid arthritis

PsA: psoriatic arthritis

SpA: axial spondyloarthritis

PROM: patient-reported outcome measures

PRO: patient-reported outcome

VAS: Visual Analog Scale

HAQ: Health Assessment Questionnaire

PASS: Patient Acceptable Symptom State

BASDAI: Bath Ankylosing Spondylitis Disease Activity Index

BASFI: Bath Ankylosing Spondylitis Functional Index

BOYD: Bring Your Own device

DANBIO: the Danish Rheumatology Database

nemID: personal ID

CPR: civil registration number

LU: [name]

NSK: [name]

MID: Minimal Important Difference

MCID: Minimal Clinically Important Difference

DAS28crp: Disease Activity Score28crp

ASDAS: Ankylosing Spondylitis Disease Activity Score

CRP: c-reactive protein

RC: [name]

e-CRF: electronic Case Report Form

GLM: general linear model

GCP: Good Clinical Practice

Clinical Trials number: NCT03486613

3. BACKGROUND

Rheumatoid arthritis (RA), psoriatic arthritis (PsA) and axial spondyloarthritis (SpA) are three major inflammatory arthritic diseases in Rheumatology. Since the 1980's, patient-reported outcome measures (PROM) have been used in clinical research and later on in daily clinical practice as an essential tool to evaluate the patient's perception of arthritis activity (1). PROM are important in monitoring disease activity as they capture the dynamic clinical presentation of RA, PsA and SpA with symptoms that cannot be measured objectively e.g. pain, fatigue and morning stiffness of the joints. As advised by the Food and Drug Administration in "Patient-reported outcome (PRO) Guidance for the Industry", PRO instruments should be used when measuring concepts best known by the patient or best measured from the patient's perspective (2). In Rheumatology in Denmark, patients are monitored using the following PROM: Visual Analog Scale (VAS) for pain, fatigue and global health (appendix 1), Health Assessment Questionnaire (HAQ) (appendix 2), Patient Acceptable Symptom State (PASS) (appendix 3), Anchoring question (appendix 4) and for patients with axial involvement: Bath Ankylosing Spondylitis Disease Activity Index (BASDAI) (appendix 5) and Bath Ankylosing Spondylitis Functional Index (BASFI) (appendix 6).

Initially, PROM was collected in a paper form. In Denmark, PROM has been registered electronically through a touch screen solution in the outpatient clinic since 2006. It has previously been shown in a Danish rheumatic patient population, that data collecting of PROM through an electronic touch screen versus paper based forms yields comparable results (3,4). Using electronic data collection of PROM has major advantages in terms of more accurate and complete data, minimisation of errors, avoidance of secondary data entry errors, less administrative burden etc. (5). During the past years, a new approach of electronic data collection of PROM is emerging called Bring Your Own device (BOYD). In medical research, BOYD means allowing participants to use their own computer device, e.g. smartphone, tablet, laptop, to access and respond to study-related PROM (5). Thus, due to the widespread use of smartphones it is now possible to use the participants' own device for collecting PROM data via a downloaded smartphone app. The participant runs the app on his/her smartphone and completes the PROM; thereafter, the data is transmitted via the internet to a specific database. Using a smartphone app instead of the traditional touch screen solution in the outpatient clinic will eliminate problems as queue, lack of discretion and uncomfortable position during data entering etc. The major advantage to collecting PROM through a smartphone app is thus, that data can be collected when and where it suits the individual patient best, thereby possibly providing more accurate answers and minimising recall-bias (5). In addition, the smartphone app ensures that the PROM questionnaires will be displayed in a relatively consistent manner independent of the different smartphone models and

has the advantages of data entry without internet connection (i.e. data will be stored in the smartphone

app and then transmitted to the database when the smartphone has internet connection) compared to

a web-based BOYD data collection. One possible disadvantage to collecting PROM through a

smartphone is distractions in the unsupervised setting e.g. telephone call, receiving/sending text mes-

sages, interaction on social media etc., which can interrupt the PROM data collection. Another barrier

is that not all adults own or has access to a smartphone and that smartphone ownership may vary

based on age, income, education etc., which means that this data collection option is not a possibility

for everyone. However, it is expected, that this solution could be a preferred possibility for some

patients. Thus, this study will assess the validity of PROM registration in the Danish Rheumatology

Database (DANBIO) through the DANBIO app on a smartphone compared to the traditional touch

screen solution in the outpatient clinic in patients with RA, PsA and SpA in standard clinical care.

4. HYPOTHESIS

Use of a smartphone app for registration of PROM in Rheumatology yields comparable results with

the traditional touch screen solution in the outpatient clinic.

5. OBJECTIVE

To evaluate whether electronic reporting of PROM through a smartphone app is comparable to the

traditional touch-screen solution in the rheumatology outpatient clinic among patients with RA, SpA

and PsA in standard clinical care. This study will thus assess the validity of registration of PROM in

DANBIO through a smartphone app.

6. METHODS

6.1. Study design

The study is a randomised, within-participants cross-over design including patients with RA, PsA and

SpA. The participants will be randomised in ratio 1:1 to group AT ($App \rightarrow Touch$ i.e. data is reported

through the smartphone app first and thereafter the touch screen) or group TA ($Touch \rightarrow App$ i.e. data

is reported through the touch screen first and thereafter the smartphone app).

Side 6 af 27

6.2. Participants

This study will include 60 participants distributed as follows: 20 participants with RA, 20 participants

with PsA and 20 participants with SpA from the rheumatology outpatient clinic at Aalborg University

Hospital. Eligibly participants will be recruited after submission and approval of the protocol to rel-

evant authorities. Recruiting will start January 2018 and continue until the target population is

achieved (presumably no longer than 3 months).

6.3. Eligibility criteria

6.3.1. Inclusion criteria

A participant will be eligible for study participation if he/she meets the following criteria:

• Diagnosed in DANBIO with RA, PsA or SpA

• Is currently treated and monitored at the rheumatology outpatient clinic at Aalborg University

Hospital

• Have previously reported PROM in DANBIO through the touch screen solution at the rheu-

matology outpatient clinic ≥ 3 times

6.3.2. Exclusion criteria

A participant cannot be included in the study if he/she meets any of the following criteria:

Inability to provide informed consent or unwilling to comply with the study protocol

• Diagnosis of RA, PsA or SpA \leq 12 months

• Does not have access to a smartphone that can download and run the DANBIO app

• Not able to understand written Danish i.e. cannot understand the Danish version of the PROM

questionnaires

Reduced sight in such degree that the participant cannot read the questionnaire in the

smartphone app/on the touch-screen with e.g. glasses

6.4. Interventions

Participants will be randomised by diagnosis to one of two groups 1:1 meaning 10 participants with

RA, 10 participants with PsA and 10 participants with PsA in each of the two groups:

Group AT $(App \rightarrow Touch)$: the participant reports data through the DANBIO app on a

smartphone first and after a "washout period" of one day via the touch screen solution at the

rheumatology outpatient clinic.

Side **7** af **27**

Group TA ($Touch \rightarrow App$): the participant reports data through the touch screen solution at the rheumatology outpatient clinic and after a "washout period" of one day via the DANBIO app on a smartphone.

6.5. Registration of PROM in DANBIO

The participants are informed about how to register data in DANBIO through the DANBIO app during the recruitment telephone call, see section 7.2. Recruitment procedures. In addition, the start date of the first data registration is decided with the patient (and noted in DANBIO). Data registration through the DANBIO app can be done when the patient has logged on with his/her personal ID (nemID). Data registration through the touch screen solution in the rheumatology outpatient clinic is done with the patient's individual civil registration (CPR) number as usual. In the rheumatology outpatient clinic, the participants will as usual answer the questionnaires in DANBIO through the touch screen. For data registration through the DANBIO app, the participants must download the DANBIO app on a smartphone with internet connection. The questionnaires answered in the DANBIO app is the same as the patients answer through the touch screen solution at the rheumatology outpatient clinic. After the participant has entered data through both methods, the participant is asked which solution is preferred: touch screen solution in the rheumatology outpatient clinic or entering data in the DANBIO app on a smartphone or no preference.

Before the first data entry of PROM, the participant must be instructed about:

- Data entering through the DANBIO app must be done within a short timeframe i.e. the participant must not do anything else during the data entry, which could be a disturbing element
- Data entering through the touch screen solution in the rheumatology outpatient clinic must be during normal opening hours i.e. 8.00-15.00 Monday to Friday.
- The first and second data registration must not be done on the same day, as there shall be a "washout period" of one day between the two data registrations. It is preferred, that the data entry occurs at the same time of the day (to avoid daytime variations in arthritis symptoms)
- The participant will receive a SMS reminder about the scheduled data entry the day before and on the day of each data registrations. On the day after the scheduled data entry, the participant will receive a SMS reminder if he/she has not completed the data entry – if the registration is not done within one day PhD student [name] (LU) will contact the participant by telephone

The participant will receive a link to the DANBIO app in AppStore or GooglePlay together

with the SMS reminder of the scheduled data entry in the DANBIO app.

The data, which the participant register, is NOT used for treatment i.e.:

• If the patients is feeling ill, he/she must seek medical treatment

In case of a soon scheduled visit in the rheumatology outpatient clinic, the participant must

re-enter his/her data in DANBIO

The data entry must not be made in relation to a doctor or nurse visit in the rheumatology outpatient

clinic as this may involve change in the patient's medical treatment or otherwise cause change in the

disease activity or the patient's perception of the disease. However, data entry may be done in con-

nection with scheduled blood sampling, scheduled X-rays or retrieval of medicine etc.

[name] (NSK) creates a dedicated page in DANBIO for this project, where all study related

data will be collected.

6.6. Set up

PhD student LU is responsible for patient recruitment, informing the participants about the study and

collecting the informed consent. LU will also provide technical support to participants if IT problems

with the smartphone app occur as explained in the participant information material.

Zitelab can be contacted by research personnel for technical support, contact person is NSK.

LU will inform staff at the Rheumatology Department at Aalborg University Hospital about the study

before inclusion of patients.

6.7. Outcomes

In this study, the PROMs listed in table 1 will be collected for the different disease groups (RA, PsA

and SpA). The Minimal Important Difference (MID)/Minimal Clinically Important Difference

(MCID) for the different measures are consistent with data presented previously (3,6–9).

This study will also estimate Disease Activity Score28crp (DAS28crp) using a fixed level for C-

reactive protein (CRP) level of 6, swollen joint count of 0.5 and tender joint count of 1 and Ankylos-

ing Spondylitis Disease Activity Score (ASDAS) using a fixed level for CRP of 6. These data are

based on DANBIO registrations of patients with RA, PsA or SpA from the rheumatology outpatient

clinic at Aalborg University Hospital. In this study, DAS28crp and ASDAS are estimated from the

PROM data to give the clinician an overview of PROM correlating to e.g. remission or high disease

activity.

Side 9 af 27

Clinical Trials number: NCT03486613

Table 1: overview of patient-reported outcome measures in this study

Variable	Disease area	Unit (range)	Aims to assess	MID/MCID	Equivalence margin
HAQ	RA/PsA/SpA	Points (0-3)	Physical function	0.22 points	± 0.11 points
VAS pain	RA/PsA/SpA	mm (0-100)	Pain intensity	10 mm	± 5 mm
VAS fatigue	RA/PsA/SpA	mm (0-100)	Fatigue severity	10 mm	± 5 mm
VAS global health	RA/PsA/SpA	mm (0-100)	Impact on global health	10 mm	± 5 mm
BASDAI	SpA	Points ¹ (0-100)	Disease activity	10 points	± 5 points
BASFI	SpA	Points ¹ (0-100)	Physical function	10 points	± 5 points
PASS	RA/PsA/SpA	Yes/No	Acceptable symptom state	N.A. ²	± 15% points
Anchoring question	RA/PsA/SpA	Transition scale	Change in arthritis activity	N.A. ²	± 1 unit AND
		(much worse [-3]-much better [+3])			± 15% points better
DAS28crp ^{3,4}	RA/PsA	Points (0.96-9.4)	Disease activity	1.2 points	± 0.6 points
ASDAS ³	PsA ¹ /SpA	Points $(0.6-\infty^5)$	Disease activity	1.1 points	± 0.6 points

^{1:} as used in the DANBIO registry

²: not applicable

³: will be estimated using a fixed level for CRP of 6

^{4:} will be estimated using a fixed level for tender and swollen joint count respectively 1 tender joint and 0.5 swollen joint

⁵: no upper limit for ASDAS

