Data will be analysed using SAS Proc Mixed. The MIXED procedure fits a variety of mixed linear models. A mixed linear model is a generalization of the general linear model (GLM); the generalization being that the data are permitted to exhibit correlation (i.e., from two measures on the same participant). Having a continuous outcome as the dependent variable (e.g. HAQ), our modelling component of SAS PROC MIXED will include both fixed (period [I or II]; questionnaire [App or Touch]; rheumatic condition [RA or PsA or SpA]) and random participant (i: 1, 2, 3,, n = 60) effects. In case of missing data for some of the participants, PROC MIXED handles the missing values implicitly adjusting for the missing values; unlike a GLM approach a mixed linear model uses the data for the periods where there is data and ignores the periods for which there is no data (10). Provided the data are "missing at random", the estimates from PROC MIXED are valid (e.g., the missing data cannot caused by some event happening during the first questionnaire exercise) (11). Imputations will not be used to replace missing data in the primary analyses, but will potentially be included in a sensitivity analysis to assess the impact/robustness of the conclusions.

Statistical interpretation of agreement: According to Piaggio et al. (12), equivalence is declared if the entire 2-sided 95%CI is included within the equivalence margin. Therefore, in this study a 2-sided 95% CI for the paired difference in each individual PROM (e.g HAQ) will be derived from the mixed linear model and agreement will be declared if the 95% CI of difference between PROMs is within the prespecified equivalence range (e.g., -0.11 HAQ-points to +0.11 HAQ-points). These margins (Table 1) are based on half of the effect that is usually considered a clinically relevant reduction in the individual PROMs. Thus, based on a superiority approach it was decided *a priori* that a 95% CI

excluding differences between groups of greater than half the MID/MCID units would be interpreted

as indicating the absence of a clinically meaningful difference (agreement) (13). No interim analyses

will be performed. All reported P values will be two-sided, based on a superiority assumption, and

will not be adjusted for multiple comparisons.

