Appendix 7: DAS28crp

DAS28crp are a composite score based on 28 joint count for tenderness and swelling, patient VAS global health and CRP level. The DAS28crp formula are:

Clinical Trials number: NCT03486613

 $DAS28crp = 0.56\sqrt{(TJC28) + 0.28\sqrt{(SJC28) + 0.36ln(CRP + 1) + 0.014(GH) + 0.96}}$

TJC28: 28 joint count for tenderness SJC28: 28 joint count for swelling CRP: C-reactive protein in mg/L

GH: patient global assessment of disease activity from 0-10 on the 100 mm VAS scale

The scoring range for DAS28crp are:

High disease activity: DAS28crp ≥ 5.1

Moderate disease activity: DAS28crp = 3.2-5.1

Low disease activity: DAS28crp = 2.6-3.1

Remission: DAS28crp < 2.6

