Appendix 8: ASDAS

Clinical Trials number: NCT03486613

ASDAS are a composite score based on patient VAS back pain, patient VAS morning stiffness, patient VAS peripheral joint pain and/or swelling, patient VAS global health and CRP level. The ASDAS formula are:

ASDAS = 0.12*Back Pain + 0.06*Morning Stiffness + 0.11*Patient Global + 0.07*Peripheral Pain/Swelling + 0.58*Ln(CRP+1)

Back pain: assessed by the patient on a 100 mm VAS scale (range 0-10)

Morning Stiffness: assessed by the patient on a 100 mm VAS scale (range 0-10)

Patient Global: assessed by the patient on a 100 mm VAS scale (range 0-10)

Peripheral Pain/Swelling: assessed by the patient on a 100 mm VAS scale (range 0-10)

Ln: natural logarithm

CRP: C-reactive protein in mg/L

The scoring range for ASDAS are:

Very high disease activity: ASDAS > 3.5

High disease activity: ASDAS = 2.1-3.5

Moderate disease activity: ASDAS = 1.3-2.0

Remission: ASDAS < 1.3

Statistical Analysis Plan (SAP): Randomised Crossover Trial

Patient-reported outcome measures collected in DANBIO reported via a smartphone app vs a touchscreen solution in an outpatient clinic among patients with inflammatory arthritis: A randomised, crossover, agreement study

Short title: The DANBIO app versus touchscreen agreement trial

[name]^{1,2,3}, [name]^{3,4}, [name]¹, [name]^{1,5}, [name]^{6,7}, [name]⁸, [name]⁸, [name]⁹, [name]¹

Affiliations

- ¹: Department of Rheumatology, Aalborg University Hospital, Aalborg, Denmark
- ²: The DANBIO Registry, Center for Rheumatology and Spine Diseases, Centre of Head and Orthopedics, Rigshospitalet, Glostrup, Denmark.
- ³: Musculoskeletal Statistics Unit, The Parker Institute, Bispebjerg and Frederiksberg Hospital, Copenhagen, Denmark
- ⁴: Research Unit of Rheumatology, Department of Clinical Research, University of Southern Denmark, Odense University Hospital, Denmark.
- ⁵: Department of Clinical Medicine, Aalborg University, Aalborg, Denmark
- ⁶: Department of Rheumatology, Aarhus University Hospital, Aarhus, Denmark
- ⁷: Department of Clinical Medicine, Aarhus University, Aarhus, Denmark
- 8: Zitelab ApS, Copenhagen, Denmark
- ⁹: Nuffield Department of Orthopaedics, Rheumatology and Musculoskeletal Sciences, University of Oxford, Oxford, UK.

Section 1: Administrative Information

Title and trial registration

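### The DAS28crp equivalence margin of ±0.6 tolerates a 43 mm shift in VAS global, its only varying input, and the ASDAS margin departs from the plan's half-MID rule

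*Protocol*

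**What the plan says.** Protocol section 6.7 states that DAS28crp will be estimated with C-"reactive protein (CRP) level of 6, swollen joint count of 0.5 and tender joint count of 1", and ASDAS with CRP fixed at 6. It says the two scores are there to give the clinician an overview.

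Table 1 in the same section gives:

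| Outcome | MID/MCID | Equivalence margin |
|---|---|---|
| VAS global health | 10 mm | ±5 mm |
| DAS28crp (RA/PsA) | 1.2 | ±0.6 |
| ASDAS (PsA/SpA) | 1.1 | ±0.6 |

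Section 6.10 explains the margins: "These margins (Table 1) are based on half of the effect that is usually considered a clinically relevant reduction". It declares agreement on a PROM when the two-sided 95% CI for the paired difference lies inside its range. The SAP repeats the same margins in its Table 2 and lists both scores, with a difference and 95% CI, in its outline comparison table.

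The DAS28crp formula in Appendix 7 ends in "0.36ln(CRP + 1) + 0.014(GH) + 0.96" and defines its patient-reported term as "GH: patient global assessment of disease activity from 0-10 on the 100 mm VAS scale". Appendix 8 gives ASDAS four patient-reported items, each scored 0-10, with weights 0.12, 0.06, 0.11 and 0.07, plus a CRP term.

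Neither score appears among the outcomes in sections 6.7.1 and 6.7.2.

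**The concern.** The device can change only what the patient enters. For DAS28crp that is a single item, VAS global, which already has its own row and margin in Table 1. DAS28crp then judges the same answers a second time on a rescaled axis, with a margin taken from the MCID of the complete score. If the rescaled margin is much wider than the item's own, the second test can hardly give a negative answer. The report could then state that the app and touchscreen agree on disease activity while the only varying input to that score fails to agree.

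The ASDAS margin raises a smaller question: it does not follow from the rule the protocol gives for all Table 1 margins.

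**Working it through.** **Inputs.** Fixed values, MCIDs and margins come from section 6.7 and Table 1. The formulas come from Appendices 7 and 8, reading each square root in Appendix 7 as covering its own joint count. The plan gives no power figure or SD for either composite, so there is none to reproduce for them. The paired equivalence power function used below does reproduce the plan's HAQ figures (90.2%, 80.7% and 99.2% for 36, 29 and 60 pairs).

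**1. DAS28crp as a function of VAS global.**

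Constant part: 0.56·√1 + 0.28·√0.5 + 0.36·ln(7) + 0.96 = 2.42.

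DAS28crp = 2.42 + 0.014·GH, so the app-minus-touchscreen difference is 0.014 × the GH difference. In the same patients this holds exactly for estimate and CI alike.

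**2. The margin on the VAS scale (GH in mm).**

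- 0.6 / 0.014 = 42.9 mm
- 42.9 / 5 = 8.6 times the VAS global margin
- ±5 mm on VAS global corresponds to 5 × 0.014 = ±0.07 on DAS28crp

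**3. A case where the two rows disagree.** A VAS global CI of +10 to +20 mm lies wholly outside ±5 mm. On DAS28crp it is 10 × 0.014 = 0.14 to 20 × 0.014 = 0.28, well inside ±0.6.

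**4. How often agreement would be declared.** This uses the 95% CI rule. The SD of the paired VAS global difference is an assumption, shown as a range, because the documents give none.

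| n | True shift | SD 10 mm | SD 20 mm | SD 30 mm |
|---|---|---|---|---|
| 20 | 10 mm | 1.00 | 1.00 | 0.996 |
| 20 | 20 mm | 1.00 | 0.998 | 0.898 |
| 40 | 20 mm | 1.00 | 1.00 | 0.997 |

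For every cell, the probability that VAS global meets its own ±5 mm margin in the same patients is 0.00 to two decimals.

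**5. The literal reading of Appendix 7.** If GH really ran from 0 to 10, the largest possible difference would be 10 × 0.014 = 0.14, and ±0.6 could not be exceeded.

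**6. ASDAS.**

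- Half-MCID rule: 1.1 / 2 = 0.55. The stated 0.6 is 0.6 / 0.55 = 1.09 times that. The other Table 1 rows with an MCID follow the rule (0.22→0.11, 10→5, 1.2→0.6).
- Sum of patient-reported weights: 0.12 + 0.06 + 0.11 + 0.07 = 0.36 per 10 mm.
- 0.6 / 0.36 = 1.67 units, or 16.7 mm if all four items shift together. With 0.55 it is 15.3 mm.

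Probability of declaring agreement with ±0.6 and n = 20, for assumed SDs of the weighted-mean item difference:

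| True shift, all four items | SD 10 mm | SD 15 mm | SD 20 mm |
|---|---|---|---|
| 0 mm | 1.00 | 0.99 | 0.88 |
| 10 mm | 0.81 | 0.47 | 0.29 |
| 15 mm | 0.11 | 0.07 | 0.05 |

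The ASDAS test is lenient at small shifts but can fail.

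**The case against.** The strongest defence is that the composite answers a different question. CRP and joint counts do not depend on the reporting device. If each patient's own measured values were used for both registrations, the DAS28crp difference would still be 0.014 times the VAS global difference. Asking whether the device moves DAS28crp by half its own MCID is legitimate, and different answers at item and composite level need not contradict each other. This stands in part. The cause is the small weight of patient global together with non-PROM inputs shared by both devices, not the particular constants chosen. It does not rescue the test, because an answer that is close to certain in advance is not evidence of agreement.

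The defence is also right that neither score is a listed primary or secondary outcome and that section 6.7 calls them an overview. Even so, Table 1 gives both an equivalence margin, and section 6.10 uses the Table 1 margins to declare agreement.

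Three stronger readings are tempting and are not supported:

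- **That the ASDAS test cannot fail either.** Only CRP is fixed. The other four inputs are patient-reported, and the second table above shows failure at moderate shifts or larger SDs.
- **That these rows act as gates that always open in the SAP's sequential procedure.** The protocol makes no multiplicity adjustment. The SAP stops at the first failure and points to its Table 2, where VAS global precedes both composites. If that row order is the sequence, a failed VAS global ends it before DAS28crp is reached. The conflicting pair of conclusions therefore arises under the protocol's own unadjusted rule.
- **That ASDAS should have a margin of 0.36 × 0.5 = ±0.18 to mirror ±5 mm.** Table 1 sets no margin for back pain, morning stiffness or peripheral pain as separate items, so the documents give no basis for it.

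The ASDAS gap of 0.05 may simply be rounding to one decimal.

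**Conclusion.** The point holds for DAS28crp. Its ±0.6 margin equals ±42.9 mm on its only varying input, against ±5 mm for that input in the same table, so an agreement claim could hardly be contradicted by the data and adds nothing to the VAS global result. This conversion needs no assumption beyond GH being in mm; on the literal 0-10 reading the test is emptier still. Only the probabilities rest on assumed SDs.

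For ASDAS, the finding is limited to a margin 9% wider than the stated rule gives, in a test that is lenient but can fail.

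A reader might infer that the trial's main conclusion is at risk. It is not: HAQ, the listed secondary outcomes and the sample size do not depend on either composite. Severity is minor to moderate.

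**What to change.** 1. Delete the DAS28crp equivalence margin from Table 1 (and from SAP Table 2) and report the score descriptively by device. This matches its overview purpose in section 6.7 and its absence from section 6.7.2. State that with the fixed inputs and GH in mm it can only run from 2.42 to 2.42 + 1.40 = 3.82, so the 5.1 cut-off for high disease activity in Appendix 7 cannot be reached.
2. For ASDAS, either report it descriptively as well or correct the margin to ±0.55.
3. Reconcile the scale of patient global in Appendix 7 (0-10 against a 100 mm scale) with the 0-100 mm range in Table 1, so that the 0.014 weight is applied to one defined unit.

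The cost is an edit to two table rows and one appendix line. One uninformative equivalence claim is lost, and no data collection changes.
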